Utilization of a wearable alcohol biosensor. To facilitate dissemination of this intervention, we will use a wearable alcohol biosensor to monitor alcohol use. Wearable alcohol biosensors are devices that can be passively worn by individuals in their daily lives and can provide a continuous measure of alcohol use. NIAAA recently announced the winners of the *Wearable Alcohol Biosensor Challenge*, which was issued to stimulate public and private investment in development and refinement of these devices (www.challenge.gov/challenge/a-wearable-alcohol-biosensor/). The proposed research will select the most appropriate biosensor from the available options. For example, the Secure Continuous Remote Alcohol Monitor (SCRAM) is an ankle bracelet that can be worn continuously, including in the shower, and includes features that allow for detection of removal and tampering. It provides an estimate of blood alcohol concentration by sampling alcohol vapor just above the skin, and also measures changes in skin temperature and skin reflectivity, which are used to detect device removal and tampering. These data are stored on the bracelet and transmitted wirelessly via a modem. Transmitted data are encrypted and stored in a web-based system called SCRAM_{NET}, which research staff can access to monitor alcohol use. BACtrack Skyn is a wrist bracelet that also provides an estimate of blood alcohol concentration by sampling alcohol vapor just above the skin. The bracelet can measure changes in skin temperature, which can be used to detect removal or tampering. Data are stored on the bracelet and can be transmitted

wirelessly via Bluetooth using a smartphone. Transmitted data are encrypted and stored in a web-based system provided by BACtrack, which research staff can access to monitor alcohol use. The proposed research will be the first to use a wearable alcohol biosensor to apply employment-based abstinence reinforcement as a therapeutic intervention.

The cost-effectiveness and cost-benefit of IPS plus abstinence-contingent wage supplements. We expect that costs of IPS plus abstinence-contingent wage supplements will be comparable to buprenorphine maintenance (Schackman et al., 2012) and less expensive than extended-release naltrexone (Kennedy et al., 2011). We will assess the costs, cost-effectiveness, and cost-benefits of IPS Plus Abstinence-Contingent Wage Supplements. [name] and [name] (Co-Is), experts in economic analyses, will conduct these analyses.

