To increase the chance that we engage participants, upon enrollment, participants will be invited to participate in a 1-week Therapeutic Workplace induction period. During the induction period, participants will be asked to maintain contact with Therapeutic Workplace staff by calling or texting staff every weekday. We have used similar induction procedures in our prior studies to successfully engage participants. Participants will be able to earn \$20 per weekday for maintaining contact with our staff during the induction period. Participants who complete the 1-week induction will be given a wearable alcohol biosensor, invited to call in to the Therapeutic Workplace every weekday for 3 weeks, and can earn about \$32/weekday for participating in our job-skills training program. Participants will be taught about the Therapeutic Workplace. Some or all of the training may be given through a computer-based training program. We may also evaluate the effectiveness of the training program by giving participants tests before and after they complete parts or all of the training program. We may re-administer the test at the end of the intervention to measure retention. Each Therapeutic Workplace participant will have a participant ID, which will be used to enter participant drug and alcohol testing results into our therapeutic workplace software, automatically implement any responses to drug and/or alcohol use based on testing results, and to automatically calculate participant daily pay based on compliance with drug and/or alcohol contingencies. Participants will be required to wear their wearable alcohol biosensor (SCRAM or BACtrack Skyn), which will record transdermal alcohol concentrations. Participants will be given separate care and use information about their wearable alcohol biosensor. Participants who wear a SCRAM bracelet will need to come to the Therapeutic Workplace (about every 30 days) so that the data stored on their bracelet can be transmitted to SCRAM_{NET} and accessed by our research staff. Participants who wear a BACtrack Skyn bracelet will need to transmit the data stored on their bracelet via Bluetooth using a smartphone. At the end of Phase 1, participants will be randomly assigned to groups.

Experimental Design

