Abstinence monitoring using SCRAM or BACtrack Skyn. Each participant will be paid for wearing a wearable alcohol biosensor (SCRAM or BACtrack Skyn). SCRAM will measure transdermal alcohol concentrations every 30 minutes. Infrared signals and temperature also will be recorded to ensure that no tampering or device removal occurs. Data recorded by SCRAM will be transferred wirelessly to a modem installed in our laboratory, which will transfer the data to a secure central server operated by the developers of SCRAM. These data can then be accessed via SCRAM_{NET}, a secure, web-based platform where all data are stored, including information on alcohol consumption, monitor obstructions or tampering, and the functioning of the battery and equipment. Participants may need to attend the Therapeutic Workplace (about every 30 days) so that data stored on their bracelet can be transmitted to SCRAM_{NET} and accessed by our research staff. BACtrack Skyn can measure transdermal alcohol concentrations every second. Temperature will be recorded to capture potential tampering or device removal. Data recorded by BACtrack Skyn will be transferred wirelessly via Bluetooth to a secure portal operated by BACtrack. If participants do not have a smartphone that is capable of transmitting the data via Bluetooth, we may provide them with one to use during their study participation. Participants will need to remove their BACtrack Skyn bracelet to shower or bathe. Participants must receive permission to remove their bracelet by sending research staff a photo or video of themselves wearing the bracelet after they put it back on. Bracelet removal cannot exceed 60 minutes. To earn the maximum in wage supplements, participant's transdermal alcohol concentrations must not test positive for alcohol at any point between the last and the current data transmission.

Resetting the wage supplement value. If a participant removes their wearable alcohol biosensor without permission or provides a transdermal alcohol concentration reading that is positive for alcohol, the value of the wage supplement will be reduced to \$1 per hour. The value of the wage supplement will be increased by \$1 per hour for every day that the participants wear their wearable alcohol biosensor and provide transdermal alcohol concentration readings that are negative for alcohol.

Usual Care Control Group

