Participants assigned to the Usual Care Control group will be offered counseling and referrals to employment and treatment services, and will be paid (see below) for wearing a wearable alcohol biosensor (SCRAM or BACtrack Skyn) for 6 months.

Standard Treatment Services

Participants in this research will have completed an inpatient alcohol detoxification at the Chemical Dependency Unit (CDU) or will be referred to treatment at the CDU, if necessary. The CDU is a 20-bed inpatient acute detoxification program for drug and/or alcohol addiction.

We will provide appropriate referrals to address patient needs in the areas of housing, and mental and medical health. Most importantly, we will assist patients in finding shelter/housing and encourage them to use Therapeutic Workplace earnings to pay for shelter. We will attempt to guide patients to seek available social service benefits, and to utilize Baltimore City's network of emergency shelters, transitional shelters, and motel placements, as needed. We may provide participants with transportation via Lyft or Uber, and cover transportation costs, when participants are traveling to and from our research unit.

Other Training and Employment Activities

Academic and computer skills training. Participants may have access to training in typing, keypad, general computer use, reading, spelling, math, GED preparation, and the use of Microsoft computer applications. We may evaluate the effectiveness of the academic and computer skills training programs by giving participants tests, such as the Wide Range Achievement Test, before and after participants complete a portion of or the entire training program.

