Participants will be removed from the study if they threaten the safety of CLH staff or other research participants, or of any other persons on the Johns Hopkins Bayview Campus.

g. Description of what happens to participants receiving therapy when study ends or if a participant's participation in the study ends prematurely.

Throughout the study, participants will be given referrals to services they might need (e.g., drug counseling, housing, medical, or employment services).

5. Inclusion/Exclusion Criteria

Inclusion criteria: a) 18 to 55 years old; b) homeless at the time of intake as defined by the McKinney-Vento Homeless Assistance Act (lacked a fixed, regular, and adequate nighttime residence including staying in a shelter, on the street, in an abandoned house or building, a car, or a park); c) unemployed; d) meet DSM V criteria for alcohol use disorder; and e) interested in obtaining employment. Exclusion criteria: a) report current suicidal/homicidal ideation; b) currently have nickel or other metal allergies, deep vein thrombosis, or leg ulcers where the SCRAM bracelet should be placed. Individuals excluded from the study will be linked with appropriate care as needed.

6. Drugs/ Substances/ Devices

NA a. The rationale for choosing the drug and dose or for choosing the device to be used.

NA b. Justification and safety information if FDA approved drugs will be administered for non-FDA approved indications or if doses or routes of administration or participant populations are changed.

NA c. Justification and safety information if non-FDA approved drugs without an IND will be administered.

NA

7. Study Statistics

a. Primary outcome variable.

Biologically-Verified Alcohol Abstinence (primary aim). Assess the effectiveness of *IPS Plus Abstinence-Contingent Wage Supplements* in promoting biologically-verified alcohol abstinence during the intervention. We will assess the number of days of alcohol abstinence (based on transdermal alcohol concentrations) during the 6 months after random assignment. Primary Hypothesis: Our primary hypothesis is that *IPS Plus Abstinence-Contingent Wage Supplements* will promote alcohol abstinence during the intervention after random assignment relative to Usual Care Control.

b. Secondary outcome variables.

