regression and GEE will be expressed using odds ratios with 95% CI. Analyses will include all randomized participants as intent-to-treat, and will be adjusted for pre-specified covariates used for stratification (Pocock et al., 2002). Tests will be two-sided and, because we have one primary outcome, alpha will be set at 0.05. Based on our previous experience, we expect rates of attrition at monthly visits to be low. If rates are higher than expected, we will use mixed effects models rather than GEE estimation, as the former has less strict assumptions regarding missing data (MAR, rather than MCAR). If it appears that the missing data are MNAR, then we will fit pattern mixture models as described by Hedeker & Gibbons (1997).

Missing data. We expect to collect >90% of assessments. Our approach to handle missing data will be to impute all missing values as the adverse outcome (e.g., alcohol positive). Model parameter estimates from this approach will be compared to a method without imputation. If these methods yield differing results, conclusions will need to be tentative, but results from both approaches will be reported in publications. To investigate sensitivity to missing values, participants with and without missing values will be compared by covariates and treatment assignment. If rates of missingness are higher than expected, we may use multiple imputation (Rubin, 1996) or pattern mixture models (Hedeker & Gibbons, 1997) to obtain unbiased estimates of treatment effects.

Consideration Of Sex And Other Variables In Moderating The Outcomes

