Participant payment for wearing alcohol biosensor. Participants can earn daily pay for wearing their wearable alcohol biosensor. Participants can earn \$0.25 per hour for wearing their alcohol biosensor and can earn a \$5 bonus for wearing their alcohol biosensor for at least 18 hours per day. However, to receive the daily payment participants must receive permission to remove their bracelet by sending research staff a photo or video of themselves wearing the bracelet after they put the bracelet back on. In total, participants could earn a maximum of \$11 per day for wearing their biosensor.

Participant payment for assessments. Assessments will be conducted for all participants at intake to determine eligibility and characterize the population, immediately prior to random assignment, every 30 days throughout the 6-month intervention evaluation period after random assignment and then at 6 and 12 months after the end of the intervention evaluation period. Participants will be paid \$30 for the intake and monthly assessments during the 1-month training period and the 6-month intervention evaluation period, and \$50 for the assessments conducted 6 and 12 months after the end of the intervention evaluation period. In total, participants will be able to earn up to \$340 for completing the assessments in this study.

Participant referral fees. As in our previous studies, participants will have the optional opportunity to earn incentives for referring people who are interested in the study. If a referral attends the initial screening appointment and completes the necessary assessments, the participant who referred the person will receive up to \$20. If a referred person enrolls in the main study, the participant who referred the person will receive up to \$40 for making the referral.

Device Return. To help ensure that participants return their wearable alcohol biosensor bracelets after their study participation ends, participants will be able to earn \$100 for returning the bracelet to our staff.

11. Costs

a. Detail costs of study procedure(s) or drug (s) or substance(s) to participants and identify who will pay for them.

There will be no costs to participants for any services or treatment provided in this study. All procedures in the study will be paid for out of grant funds.

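### Either of two biosensors may supply the primary outcome, and device type, known before randomisation, is missing from the primary model

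*Combined protocol and SAP*

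**What the plan says.** The primary outcome (section 7.a) is the "number of days of alcohol abstinence (based on transdermal alcohol concentrations) during the 6 months after random assignment", with no device named. Section 4.a allows either device. In the control arm, for example, participants are paid "for wearing a wearable alcohol biosensor (SCRAM or BACtrack Skyn) for 6 months", and the abstinence-monitoring text says the same of each participant.

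The devices are described differently in section 3 (wearable biosensor paragraph) and section 4.a (abstinence monitoring):

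- **Sampling:** "SCRAM will measure transdermal alcohol concentrations every 30 minutes", whereas "BACtrack Skyn can measure transdermal alcohol concentrations every second".
- **Bathing:** SCRAM can stay on in the shower; Skyn has to be taken off.
- **Tamper signals:** infrared and temperature for SCRAM; temperature alone for Skyn.

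On timing, section 4.a (Therapeutic Workplace and Job-Skills Training) says "Participants who complete the 1-week induction will be given a wearable alcohol biosensor". Randomisation follows at the end of Phase 1.

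The urn factors (section 4.a, Experimental Design) are baseline percent of days abstinent by transdermal reading, opiate and cocaine use, high school or GED completion, and gender. Under Main analysis in section 7.c, analyses "will be adjusted for pre-specified covariates used for stratification". Device is in neither list, nor among the moderators later in section 7.c.

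**The concern.** Two instruments feeding one endpoint need not record the same number of abstinent days for the same drinking. Here they differ in how often they can sample, in how removal is detected and in whether daily removal is unavoidable. If they do record abstinence differently, device predicts the outcome. A predictor left out of the model has two effects: its contribution stays in the residual variance, and any chance difference in device share between arms passes into the estimated effect. Since the bracelet is issued before allocation, device could enter the model as an ordinary baseline covariate.

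**Working it through.** **The plan's own figure.** Section 7.c: 130 × 0.90 = 117 after 10% missing data, for a 15-point difference at 80% power. The arithmetic is right. The required N behind it cannot be fully reproduced, because the within-person correlation is not stated and the figure is not available. The point here does not dispute it.

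**Inputs from the plan.** 130 randomised in two arms; design difference 15 points.

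**Assumed inputs.** 1:1 allocation, so 65 per arm (the ratio is not stated). Share on one device s = 0.50, with 0.25 or 0.75 as the alternative. Difference between devices in recorded proportion of abstinent days d = 0.10 to 0.20. Between-participant SD of that proportion 0.35. The documents give none of these.

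**Step 1: chance imbalance in device share.**
SE = √[2·s(1−s)/65].
- s = 0.50: √(2 × 0.25/65) = 0.0877; × 1.96 = 0.172, about 17 points.
- s = 0.25 or 0.75: √(2 × 0.1875/65) = 0.0760; × 1.96 = 0.149, about 15 points.

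**Step 2: shift in the unadjusted arm difference.** Shift = imbalance × d.

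| Device mix | d = 10 points | d = 20 points |
|---|---|---|
| 50:50 | 0.172 × 10 = 1.7 points | 0.172 × 20 = 3.4 points |
| 25:75 | 0.149 × 10 = 1.5 points | 0.149 × 20 = 3.0 points |

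These are the edges of the 95% range, not typical values.

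**Step 3: share of variance due to device.** s(1−s)d²/SD², with SD² = 0.1225.
- 50:50: 0.25 × 0.01/0.1225 = 2.0% at d = 0.10; 0.25 × 0.04/0.1225 = 8.2% at d = 0.20.
- 25:75: 0.1875 × 0.01/0.1225 = 1.5%; 0.1875 × 0.04/0.1225 = 6.1%.

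**Step 4: effect on precision (50:50 mix).**
- Unadjusted 95% half-width: 1.96 × 0.35 × √(2/65) = 0.120, or 12.0 points.
- Adjusted, d = 0.10: 12.0 × √(1 − 0.020) = 11.9 points.
- Adjusted, d = 0.20: 12.0 × √(1 − 0.082) = 11.5 points.

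The plan's model reports odds ratios, so these percentage-point figures are a guide to size only.

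**The case against.** The strongest reply is that this is a small matter and partly handled already.

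- **Chance imbalance is not bias.** For a factor fixed before randomisation, it is already reflected in the confidence interval. This stands. What adjustment offers is a somewhat narrower interval and an estimate less exposed to the particular allocation drawn.
- **A related covariate is in the model.** Baseline percent of days abstinent comes from transdermal readings and is both an urn factor and a covariate. A device that shifts recorded abstinence shifts this baseline too, if the participant keeps the same device. That absorbs part of the device effect, but only part: the urn factor is split at a rolling median taken across both devices. The gains above are therefore upper figures under their assumptions.
- **There may be only one device in practice.** Section 3 says "The proposed research will select the most appropriate biosensor from the available options", which reads as a single choice. Section 4.a nevertheless provides for both throughout, and the mix is not stated. If all randomised participants wore the same device, the point falls away.
- **The removal rules are largely shared.** The reset for unpermitted removal (section 4.a) and the photo or video condition for pay (section 10.a) are worded for either device. The real contrasts are bathing and tamper signals.

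A reader might infer that second-by-second sampling makes false positive days far more common on Skyn. The documents do not support this. One-second sampling is given as something Skyn can do, not as the study setting, and no error rate is stated. The condition that no reading be positive at any point governs wage supplements, not the scoring of the primary outcome.

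**Conclusion.** The point holds as a modest precision issue. Device type is available before randomisation, may be related to how abstinence is recorded, and is left out of the primary model. Under the assumptions shown, leaving it out lets chance imbalance move the arm difference by at most about 1.7 to 3.4 points (95% range), and adjustment would remove about 2% to 8% of the variance, less what the baseline abstinence covariate takes up. If the true device difference is near zero, so is the gain.

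Two stronger conclusions are not supported. One is that the arms are systematically biased: the device is issued before allocation, so its expected distribution is the same in both arms. The other is a stated loss of power from misclassified days: that needs error rates by device, which the documents do not give, and a covariate would not repair it.

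**What to change.** In section 7.c, Main analysis, add the device worn at randomisation (SCRAM or Skyn) to the pre-specified covariates of the primary model. Report the treatment effect by device as a supportive check, without a separate claim. State that the term is omitted if only one device was in use. Make the change before any comparison of the groups is seen.

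The cost is one degree of freedom and a sentence or two of plan wording, with no new visits or measurements. One limit should be stated: the device at randomisation may not be the device worn later, since no section says it is kept throughout and section 8.b leaves continued SCRAM wear to the study clinician in some cases. The baseline device is still the right covariate, because a later change could depend on the arm.

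The threshold in section 10.a, "for wearing their alcohol biosensor for at least 18 hours per day", should not be taken over as a scoring rule for the outcome as part of this change. It is a payment condition. Combined with the plan's rule that missing values count as adverse, it would redefine the endpoint and could bring in differences in wear between arms.
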